1.0 Objectives

1.1 Primary Objective

To determine whether the use of a fibrin sealant applied to axillary soft tissues following node dissection can result in earlier drain removal.

1.2 Secondary Objectives

To determine the postoperative morbidity rate using fibrin sealant following axillary node dissection.

To assess patient-valuation of outcome by performing a cost-benefit analysis using a willingness-to-pay model.

To determine if serum levels, lymphatic fluids level, or cutaneous expression of vascular endothelial growth factor-D (VEGF-D), vascular endothelial growth factor-C (VEGF-C) or their receptor, vascular endothelial growth factor receptor-3 (VEGFR-3) correlates with nodal tumor burden or development of lymphedema in patients with melanoma.

2.0 Background

In 2000, 47,700 men and women were diagnosed with melanoma in the United States.¹ Many of these patients undergo axillary node dissection for staging and/or therapeutic purposes.

The most common short-term complication following axillary node dissection for patients with breast cancer or melanoma is seroma formation which may occur in up to 35% of patients.²⁻⁵ Several techniques have been used in attempts to prevent seroma formation including the use of a suction drain inserted at the time of surgical dissection^{6,7} as well as the insertion of multiple drains⁸, high and low suction drains⁹ and post-mastectomy shoulder immobilization.¹⁰

The use of drains in the postoperative period has several disadvantages. First, the drain requires proper management to assure patency. Additionally, there is associated discomfort and limited mobility with the presence of a drain. There is also a theoretical risk of infection with prolonged drainage, as a drain is thought to serve as a portal for bacterial entrance into the deep tissues.¹¹ A technique that would allow earlier drain removal or potentially eliminate the need for a drain altogether might decrease morbidity and cost while enhancing patient rehabilitation and satisfaction, and allowing earlier commencement of adjuvant therapy.

Fibrin tissue adhesive is the name given to products, originally made from plasma proteins that mimic the last step of the physiological coagulation cascade.¹² These products when applied locally to the site of "injury" are thought to enhance hemostasis, adhesion and provide a matrix for peptides to enhance wound healing. Additionally, fibrin plays a central role in wound healing by inducing chemotaxis of polymorphonuclear granulocytes and promoting the initial inflammatory phase of the healing process.¹³

Preliminary Data

Fibrin tissue adhesives have been commercially available in Europe since 1978 and have been used for numerous procedures in all fields of surgery.^{12,14}

Several randomized trials have demonstrated the utility of fibrin tissue adhesives in a variety of surgical settings. For example, randomized trials have favored fibrin tissue adhesives in the setting of intraoperative control of hepatic bleeding¹⁵ and intraoperative control of bleeding cancellous bone at sternal and iliac crest donor sites.¹⁶

However, other trials have reported conflicting results with the use of fibrin tissue adhesives. For example, in a trial of 56 patients randomized to fibrin tissue adhesive after distal pancreatectomy, there was a decrease in postoperative fistula formation from 40% to 15.4% ($p=0.04$)¹⁷ while D'andrea et al. demonstrated no difference in the rate of fistula formation between the control and fibrin tissue adhesive groups in 97 patients undergoing pancreatectomy.¹⁸

Axillary Node Dissection for Breast Cancer

Fibrin tissue adhesives have previously been shown to be effective in reducing seroma formation in animal models for mastectomy.¹⁹⁻

²² However, there have been conflicting reports of the efficacy of fibrin sealant in reducing seroma formation in humans undergoing axillary dissection.²³⁻²⁸

There have been three prospective, randomized trials in humans that have reported a benefit in using fibrin tissue adhesives in the setting of axillary node dissection for breast cancer. The first study, performed at the University of Virginia Health Sciences included 21 patients to evaluate the efficacy of fibrin sealant in decreasing total serous drainage from the axilla.²⁴ The fibrin sealant was composed of bovine thrombin and autologously donated fibrinogen. Their results demonstrated that the cumulative volume of axillary drain seroma fluid for 3 days was reduced by 268 mL or 57%. The day of axillary drain removal was reduced by 3 days or 43 percent (6.9 ± 1.19 to 3.9 ± 1.70 days in the treatment group).²⁴ Within the small group studied, this difference was statistically significant.

The second randomized trial was performed in Europe and included 108 patients with breast cancer.²³ The treatment group received 2 ml of fibrin glue applied to the area of axillary dissection following lymphadenectomy. The cumulative volume of axillary drainage for 6 days was reduced by 48% (408 ml vs. 214 ml, $p=0.001$) and the hospital stay was decreased by 21% in the treatment group. There was no difference in short-term or 6 month morbidity between the treatment and control group.²³

The third study was a phase II, multi-center, prospective randomized trial which randomized 78 patients to 4 treatment arms.²⁶ Twenty-one patients in the control group did not receive fibrin sealant while the remaining 57 patients were treated with escalating dose of fibrin sealant

(4, 8 or 16 ml). The authors reported that 4 ml of fibrin sealant is sufficient to produce a 30% reduction in median time to drain removal (14.8 ± 9.6 days vs. 7.9 ± 3.7 days) and a 23% reduction in cumulative drainage over 4 days.²⁶

There have also been 3 prospective, randomized trials that have reported that fibrin tissue adhesives are ineffective in reducing the volume of seroma drainage following mastectomy.^{25, 27, 28} Uden's study²⁵ had relaxed criteria for time to drain removal (< 100 cc/ 24 hours) which would make discrimination difficult. Dinsmore's study²⁷ included only 27 patients and used a fibrin tissue adhesive with a low concentration of fibrinogen. In the trial by Vaxman et al.,²⁸ a significant difference in the volume of seroma drainage was seen in 40 patients, however, this did not result in a difference in drain duration.

To date, there are no published prospective trials using fibrin tissue adhesive in patients with melanoma. The lack of data in patients with melanoma together with the discrepancies in the published results in patients with breast cancer indicate the need for a properly designed, randomized study. The purpose of this prospective, randomized trial is to perform a study with sufficient statistical power to determine whether fibrin tissue adhesive is truly effective in reducing the time to drain removal following axillary node dissection in patients with melanoma.

Laboratory Correlative Studies

Lymphatic spread represents the most common first site of metastasis in patients with primary cutaneous melanoma and represents a significant clinical problem with respect to both treatment as well as treatment-related complications. While it is known that the lymphatic vasculature transports extravasated fluid, macromolecules, and even cells into the systemic circulation, little is known regarding the molecular mechanisms which regulate lymphatic vessels. Recently, vascular endothelial growth factor VEGF-C and VEGF-D have been shown to stimulate lymphangiogenesis and are regulated through their common receptor, VEGFR-3.²⁹ Interestingly, recent studies have demonstrated that inhibition of VEGF-C/VEGF-D signaling may inhibit lymphangiogenesis and induce regression of already formed lymphatic vessels, as well as lymphedema-like symptoms in experimental models.³⁰ Preliminary observations suggest that VEGF-D may be overexpressed in melanoma nodal metastasis. However, the role of these growth factors in human melanoma is currently unknown.

3.0 Background Drug Information

TISSEEL® VH Fibrin Sealant, prepared by Baxter Hyland Immuno, is a two-component fibrin sealant, vapor heated kit that contains the following substances in four separate vials:

1. Sealer protein concentrate (human);
2. Fibrinolysis inhibitor solution (bovine);
3. Thrombin (human);
4. Calcium chloride solution

TISSEEL® contains Fibrinogen (Sealer Protein) as the main active ingredient. Sealer Protein Concentrate is formulated as a sterile, non-pyrogenic, freeze-dried, vapor-heated powder preparation made from pooled human plasma. TISSEEL® also contains Thrombin, Calcium Chloride, and Fibrinolysis Inhibitor (Aprotinin) Thrombin is formulated as a sterile, non-pyrogenic, freeze-dried, vapor-heated powder preparation made from pooled human plasma. Both of these components are made from pooled human plasma. The two-step vapor heat treatment used in their manufacture has been shown to be capable of significant viral reduction.

The fibrinolysis inhibitor solution (Aprotinin) is of bovine origin and is formulated as a sterile, non-pyrogenic solution containing 3,000 kallidinogenase inactivator units of Aprotinin, an inhibitor of proteases including plasmin.

When the two reconstituted components, the Sealer Protein and Thrombin Solutions, are mixed and applied topically they produce a viscous solution that quickly sets into an elastic coagulum.

3.1 Toxicity

TISSEEL® 5ml VH Kit is made from human plasma which may contain infectious agents, such as viruses, that can cause disease. The risk that such products will transmit an infectious agent has been markedly reduced using three methods: (1) screening plasma donors for prior exposure to certain viruses, (2) by testing for the presence of certain virus infections (including HIV and hepatitis), and (3) by inactivating and removing certain viruses. Although the potential risk of virus transmission can never be totally eliminated, TISSEEL® VH fibrin sealant has been used in more than 6 million surgical procedures for over 20 years with no confirmed cases of viral transmission to date.^{31,32}

As with any other plasma derivatives, anaphylactoid or anaphylactic reactions may occur in rare cases. No adverse events of this type have been reported during the course of clinical trials.

The fibrinolysis inhibitor solution (Aprotinin) TISSEEL® is of bovine origin. In cases of hypersensitivity to bovine proteins or after repeated administration, allergic or anaphylactic reactions can occur on rare occasions. TISSEEL® is contraindicated in individuals who are known to be hypersensitive to bovine protein.

4.0 Patient Eligibility

4.1 Part I - Inclusion Criteria

Patients that consent to participate.

Patients with melanoma who have undergone axillary dissection within the last six months as part of their surgical treatment will be considered for the study.

4.2 Part II - Inclusion Criteria

Patients that consent to participate.

Patients with melanoma that will be undergoing axillary node dissection as part of their operative management.

4.3 Part II - Exclusion Criteria

Patients with known hypersensitivity to bovine proteins.

Patient has undergone prior radiation therapy to the operative site.

Patient is pregnant or lactating.

Patient is steroid dependent within prior 6 months.

Patient has used aspirin or other anti-platelet drug (excluding Celebrex) within seven days of operation.

Patient has pre-existing lymphedema.

Patient has other pre-existing medical conditions with evidence of organ dysfunction as determined by principal investigator.

5.0 Treatment Plan

The protocol will consist of two parts:

Part I: Questionnaire development (pilot study)

Part II: Intervention

Part I: Questionnaire Development:

Prior to the accrual of patients on Part II, a preliminary questionnaire (see Appendix G) was given to a group of 20 patients who were identified as having already been treated at MDACC. Eligible patients had a diagnosis of melanoma and had an axillary nodal dissection performed within the last 6 months. A research nurse interviewed the 20 patients and asked a two-part questionnaire about what it was like to have a surgical drain following an axillary node dissection. The first part of the questionnaire focused on short-term lifestyle changes, averting behaviors, and expenditures related to having a drain. The second part of the questionnaire involved hypothetical scenarios of a 25% reduction in time to drain removal. The patients were asked to think about the hypothetical health benefit of early drain removal to reveal the maximum cost willing to pay in dollars for such a benefit. The questionnaire took approximately 20 minutes to complete.

The results of the preliminary questionnaire were used to create willingness-to-pay questionnaires 1A and 1B (see Appendix H) which will be administered as an option to patients in Part II of the study preoperatively (questionnaire 1A), and about 3-6 weeks postoperatively (questionnaire 1B) by the research nurse either in the clinic or by telephone interview. We will then use this information to quantitate the disutility of having a drain using a willingness-to-pay (WTP) analysis. Cost Benefit Analysis: cost (fibrin sealant, \$) - benefit (WTP, \$) = net benefit (\$). The questionnaires will take approximately 20 minutes to complete.

Part II:

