8.0 Data Collection Tools

Part I - Pilot questionnaire (Appendix G) will be used.

Part II - Data sheets (Appendices A and B) will be used to capture patient information including:

Preoperative Assessment:

Risk Factors: smoking, obesity (BMI > 30)

Prior therapy

Date of randomization

Intraoperative Assessment:

Surgeon
 Date of procedure
 Perioperative antibiotics
 Procedure performed
 Indication (i.e., after positive sentinel node biopsy or for clinically evident disease)
 Estimated blood loss
 Length of operation

Post-Operative Assessment:

Date of drain removal
 Wound complications: infection, seroma, wound necrosis or dehiscence, clogged drain, hematoma, etc.
 Final pathologic assessment: diagnosis, number of nodes examined, number of tumor involved nodes
 Tumor stage

Patients will be instructed in catheter care according to nursing protocol and given instructions on completing the drain output forms. The amount of drainage will be recorded for each day (24 hour period) including the day the drain is removed.

Part II - Willingness-to-pay preoperative questionnaire 1A and willingness-to-pay postoperative questionnaire 1B (Appendix H) will be used.

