9.0 Statistical Considerations

This is a single-institution, randomized, phase III trial of the fibrin tissue adhesive (TISSEEL®) versus no fibrin tissue adhesive (control) in patients with melanoma undergoing nodal dissection of the axilla. The primary outcome, is time-to-drain removal (T). The null median for the group based on historical experience without fibrin glue is 14 days (Table 1) with an accrual rate of 7 patients per month. A group-sequential design with up to two tests using O'Brien-Fleming early stopping boundaries for both superiority and futility will be used, with overall type I error probability .01 and power .95 will be used. The goal will be to detect a 4 day drop in mean time-to-drain removal. A maximum of 95 patients will be accrued to obtain a sample size of 90 assuming a 5% rate of patients who are inevaluable. Based on a two-sample Z-score test statistic, within in each subgroup the interim test cutoffs will be +/- 3.64 to reject the null hypothesis of no difference and +/- .632 to stop for futility, with a final test cutoff of +/- 2.57 to reject the null. The anticipated study duration will be roughly 12 months.

Table 1.

Subgroup	Disease	Type of Surgery	Accrual Rate (patients/month)	Historical Median # Days to Drain Removal
1	Melanoma	Axillary node dissection	7	14

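### The cost-benefit formula subtracts benefit from cost but labels the result net benefit, so its sign is reversed

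*Combined protocol and SAP*

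**What the plan says.** Section 1.2 lists the economic analysis as a secondary objective: "To assess patient-valuation of outcome by performing a cost-benefit analysis using a willingness-to-pay model".

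Section 5.0, under Part I, describes how WTP was elicited in the pilot. Patients were given "hypothetical scenarios of a 25% reduction in time to drain removal" and asked to consider that benefit "to reveal the maximum cost willing to pay in dollars for such a benefit". The pilot results were used to build questionnaires 1A and 1B, which Part II patients may complete before surgery and about 3 to 6 weeks after it. The answers are to be used to "quantitate the disutility of having a drain using a willingness-to-pay (WTP) analysis".

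The computing rule follows: "Cost Benefit Analysis: cost (fibrin sealant, \$) - benefit (WTP, \$) = net benefit". All three terms are in dollars.

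Two other sections might have added to this rule, but neither does. Section 8.0 says only that "Willingness-to-pay preoperative questionnaire 1A and willingness-to-pay postoperative questionnaire 1B (Appendix H) will be used". Section 9.0 deals with the primary comparison ("The primary outcome, is time-to-drain removal (T") and does not mention the cost-benefit analysis.

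**The concern.** A net benefit should rise as the benefit rises and fall as the cost rises. The quantity defined in section 5.0 does the reverse. The more patients would pay for earlier drain removal, the lower the reported figure; the more the sealant costs, the higher it is.

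The sign carries the conclusion of this kind of analysis, because it tells the reader whether patients value the outcome above or below what the sealant costs. If the rule is followed literally and the result is reported under its stated label, a reader who takes net benefit in its usual sense would draw the opposite conclusion about value for money.

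**Working it through.** The plan reports no sealant cost, WTP or net-benefit figure, so there is no number of its own to reproduce. The check is a sign check on the formula.

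**Inputs, all from section 5.0**

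- C = cost of the fibrin sealant, in dollars. The formula labels it as the cost.
- W = WTP, in dollars. The formula labels it as the benefit. The pilot description agrees: W is the most a patient would pay for earlier removal, so a larger W means a more valued outcome.

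**Formulas**

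- As the plan writes it: S = C - W.
- Net benefit: NB = W - C.
- Therefore S = -(W - C) = -NB for every C and W. The two agree only when C = W, where both are 0.
- Gap between the two: NB - S = (W - C) - (C - W) = 2 x (W - C), or 2 x |W - C| in absolute size.

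**Illustration.** The dollar values below are assumed, because the documents give none. They cover WTP above, below and equal to cost.

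| C (assumed, dollars) | W (assumed, dollars) | Plan: C - W | Net benefit: W - C | Absolute gap: 2 x abs(W - C) |
|---|---|---|---|---|
| 300 | 500 | 300 - 500 = -200 | 500 - 300 = +200 | 2 x 200 = 400 |
| 500 | 300 | 500 - 300 = +200 | 300 - 500 = -200 | 2 x 200 = 400 |
| 300 | 300 | 0 | 0 | 0 |

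The reversal does not depend on the values chosen; they set only the size of the gap.

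**Could the line be read another way?** If the dash were only a separator between two listed items, there would be no subtraction. But an equals sign and a result in dollars follow, so the line is an equation. The line is also intact, with each term carrying its own label and unit, so nothing points to a fault in the text extraction.

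**Is it corrected elsewhere?** Section 1.2 states only the objective, section 8.0 only names the questionnaires, and section 9.0 covers only the primary outcome. None gives a sign convention. Appendices G and H are not in the text available for this review and could not be checked. The protocol describes them as questionnaires, and a convention stated there would still leave the formula in section 5.0 wrong as written.

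**The case against.** The strongest reply is that this is a labelling slip in a one-line schematic. Both operands are named, so anyone doing the analysis can see which is the cost and which the benefit, and the intended meaning is hardly in doubt. No threshold, test, stopping rule or adoption rule uses the sign. The harm requires that the formula be applied literally and that the net figure be reported without its two components, and the documents do not say that either will happen. The stated aims of assessing patient valuation and quantifying the burden of the drain rest on WTP itself, which the reversal leaves untouched. Finally, no calculated number in the plan is wrong, because the plan gives none.

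Much of this stands as a limit on the consequences. Only the final net figure is affected, its absolute size is right, and a careful analyst might well notice the problem. It does not remove the error. Section 1.2 makes a cost-benefit analysis the means of meeting the objective, and the net figure is the product of that analysis. A prespecified rule should not depend on someone correcting it unprompted, and a silent correction would itself depart from the written plan.

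**Conclusion.** The concern holds. As written, the quantity labelled net benefit is net cost. Its sign is reversed whenever sealant cost and WTP differ, and it is off by twice the absolute difference between them. This follows from the formula's own labels and needs no outside source; only the dollar amounts in the illustration are assumed.

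The reach is limited to one secondary economic result, based on questionnaires that patients may decline. The primary endpoint, sample size and stopping boundaries in section 9.0 do not depend on it. Because this is the only computing rule for that objective in the available text, it should be corrected rather than left to interpretation. The statement that nothing else corrects it is subject to the absence of Appendices G and H.

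**What to change.** In section 5.0, reverse the subtraction:

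- net benefit (dollars) = benefit (WTP, dollars) - cost (fibrin sealant, dollars).

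Alternatively, keep the expression and change only the name of its result:

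- cost (fibrin sealant, dollars) - benefit (WTP, dollars) = net cost (dollars).

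Either version is enough, provided the report uses the same label and sign. The cost is a one-line wording change, with no new data and no change to the design, sample size or primary analysis.

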5.1 Preoperative

After consents for operation and study participation are signed, patients will be registered for the trial by the research nurse. Patients will be randomized using a computerized randomization scheme.

Patients will be randomized to two groups:

Group I Treatment Group: Patients will receive fibrin sealant following completion of axillary dissection.

Group II Control Group: No fibrin sealant.

The results of the randomization will remain in a sealed envelope. The surgical team will be blinded until the surgical dissection is completed.

All patients will have a 10 cc specimen of blood collected prior to surgery.

5.2 Intraoperative

Patients will be brought to the operating room within one week of randomization.

All patients will receive prophylactic antibiotic coverage at the time of surgery with Ancef or, if an allergy to cephalosporins exists, the antibiotic of choice of the surgeon.

Patients with melanoma will undergo a standard Level I-III axillary node dissection.

During surgery, a specimen of normal viable skin, full thickness, 5 mm x 3 cm from the non-margin portion or the edge of incision will be obtained. This will not impact the closure.

At the completion of the procedure, once bleeding has been controlled in the surgical site, the exposed surgical surfaces will be blotted dry. The surgeon will then be informed of the patient's randomization status.

If the patient is randomized to Group I (Treatment Group) the circulating nurse will proceed with the preparation of the TISSEEL® (Thrombin component diluted 1:100) as described in Appendix I. The product will then be applied as a thin, uniform coating over the exposed soft tissue of the chest wall and axilla.

Patients in both treatment groups will have a 19-French Blake closed suction drain inserted into the axilla and secured with a nylon suture. The wound will then be closed allowing the fibrin sealant to seal the apposed tissues.

